4.0 STUDY TREATMENTS

4.1 Treatments Administered

The starting dose of the investigational product will be determined by the study previously completed by the subject.

Subjects who completed INS011-14-029 will initiate this study on the dose with which they were being treated previously, unless tolerability issues were observed for a particular subject. Subjects who completed Part A in INS011-15-054 will continue treatment with the dose at which they were being treated previously unless a tolerability issue was observed for a particular subject.

The Sponsor has developed a dronabinol product, which has a similar chemical composition to that of Cannabidiol Oral Solution. The 2 compounds differ in that dronabinol has closed ring, while the ring is open in Cannabidiol Oral Solution. Data from a single-dose PK study of dronabinol showed a mean $t_{1/2}$ of 5.5 hours. This data supports the twice daily dosing of Cannabidiol Oral Solution.

The strength of the investigational product is discussed in Section 4.3.

Immediately after dosing, the subject will consume an adequate amount of water or clear liquid according to the age of the subject.

- For subjects aged <2 years, 4 ounces of water or clear fluid should be offered and the amount consumed recorded in the electronic case report form (eCRF).
- For subjects aged 2 to <12 years, 5 ounces of water should be offered and the amount consumed recorded in the electronic case report form (eCRF).
- For subjects aged ≥ 12 years, 8 ounces of water should be offered and the amount consumed recorded in the electronic case report form (eCRF).

The subject is not required to fast prior to or after dosing. However, the timing of meals with regards to drug administration should be consistent throughout the duration of the study.

Dosing of the investigational product may be increased or decreased based on efficacy and tolerability up to a maximum of 40 mg/kg/day.

The investigational product will be administered in an adjunctive setting and background AED medication(s) will be administered as described in Section 4.3.

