1.1.4.1 Pharmacokinetics

Oral doses of cannabidiol (10 mg/kg/day) once daily for 6 weeks in patients with Huntington's disease results in mean weekly plasma concentrations of 5.9 to 11.2 μ g/L.^{51,52} The mean t_{1/2} for cannabidiol is 24 and 31 hours when administered intravenously (IV) or inhaled, respectively, with a range of 18 to 33 hours.⁵³ Cannabidiol is cleared from plasma at rates between 960 and 1560 mL/min and the distribution volume is estimated to be approximately 30 L/kg.⁵³

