1.1.4.2 Overview of Safety

Clinical studies in various human populations indicate that cannabidiol has a favorable side-effect profile. Doses as high as 1500 mg are well tolerated.⁵⁴ No significant reactions or serious adverse events (SAEs) have been reported across a wide range of dosages and in both

acute and chronic settings. Bergamaschi et al.¹⁷ recently reviewed the safety of cannabidiol in humans examined in 221 subjects across 21 studies. As detailed in the IB, no significant safety issues were reported.

Selected studies in which more detailed information regarding safety outcomes are reviewed in Section 1.1.4.2.1.

Regarding doses of cannabidiol that have been examined in other studies, daily doses of 200 to 300 mg cannabidiol (or potentially more) may be safe.^{2,58} Clinical evaluation and therapeutic ranges of cannabidiol doses have been reported to be between 10 and 1500 mg/day, with the majority of reports evaluating doses in the 300 to 600 mg/day cannabidiol range. Furthermore, between 300 and 1500 mg have been used in humans without toxicity or SAEs.^{51,55,56,57} Cannabidiol PK has not previously been studied in a pediatric population.

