4.1.1 Dose Adjustments

IP dose may be adjusted at the investigators discretion. Dose may be adjusted up or down based on efficacy, safety or tolerability. All dose changes must be clearly documented in the eCRF. Maximum dose must never exceed 40mg/kg/day.

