6.2.1 Plasma Levels-related Endpoint

The plasma level-related endpoint is trough (steady state) concentrations of Cannabidiol Oral Solution throughout approximately 48 weeks of continuous exposure or until the investigational product is successfully approved for marketing in the US (whichever occurs earlier), inclusive of the subject's treatment on their previous study.

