Concentration data of CBD and 7-OH-CBD will be tabulated and summarized by CBD dose level (based on the daily dosing regimen, mg/kg/day, of CBD when the plasma sample is taken) at each collection time (scheduled week) using descriptive statistics (n, mean, SD, minimum, median, maximum, and percent coefficient of variation). In addition, dose-normalized concentrations of CBD and 7-OH-CBD will be tabulated and summarized by clobazam flag

Pharmacokinetic Statistical Analysis Plan
Insy Clinical Trial Protocol INS011-14-030

(yes/no) at each collection time (scheduled week) using descriptive statistics. CBD and 7-OH-CBD concentration-time data for subjects continuing on study medication as part of the Expanded Access Program will be summarized in a secondary set of tables and figures.

Concentration data of clobazam and norclobazam will be stratified by clobazam flag (yes/no), tabulated, and summarized using descriptive statistics.

In the data tabulation and summarization, concentrations below the lower limit of quantitation (BLQ) will be set to zero.

Plots of mean concentration-time for CBD and 7-OH-CBD and dose-normalized CBD and 7-OH-CBD will be created by CBD dose level, with and without stratification by clobazam (yes/no). Plots of concentration-time data for CBD and 7-OH-CBD for individual subjects will be created; since the dose level may vary during the study, the dose level at a given sample time will be labeled or foot-noted (if possible) in the figure. Plots for clobazam and norclobazam will be stratified by subjects on clobazam therapy (yes/no).

Pharmacokinetic Calculations

The metabolite-to-parent ratio (MRCtrough) will be calculated using concentrations of 7-OH CBD (metabolite) and CBD (parent) at each Visit, starting with the first trough sample obtained and through the remaining visits. If either CBD or 7-OH CBD concentration is not reportable or BLQ, MRCtrough will be reported as "not applicable". MRCtrough for clobazam will be calculated using the same methodology.

To assess the degree of accumulation during long-term BID administration of cannabidiol oral solution after 1 month treatment (Visit 5), an accumulation ratio (RCtrough) will be estimated using the dose-normalized trough plasma concentrations of CBD and 7-OH-CBD at each Visit, according to:

$$RCtrough = \text{Conc}/D(n^{\text{th}} \text{ visit dose})/\text{Conc}/D(5^{\text{th}} \text{ visit dose}),$$

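### The PK SAP puts every pre-dose sample into the by-dose tables and RCtrough with no minimum time on the current dose, although the protocol endpoint is a steady-state trough

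*Protocol*

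**What the plan says.** **Endpoint.** Protocol 6.2.1: "The plasma level-related endpoint is trough (steady state) concentrations of Cannabidiol Oral Solution". The synopsis lists the same endpoint.

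**Dose changes.** Protocol 4.1.1: "Dose may be adjusted up or down based on efficacy, safety or tolerability". The synopsis allows a change at any time at the investigator's discretion, up to the stated maximum. Changes must be documented in the eCRF.

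**Analysis.** The PK SAP (Concentration-Time Data Tabulation) summarises concentrations by dose level, "based on the daily dosing regimen, mg/kg/day, of CBD when the plasma sample is taken". Under Pharmacokinetic Calculations, RCtrough is the dose-normalised trough at a later visit divided by the dose-normalised trough at Visit 5, summarised by dose level in the same way. A ratio is withheld only if a concentration is not reportable or below the limit of quantitation. The PK population requires one usable concentration, and usable is not defined. Neither document sets a minimum time on a dose, a flag for a recent change, or an exclusion.

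**Half-lives.** Protocol 1.1.4.1 says that the mean half-life of cannabidiol "is 24 and 31 hours when administered intravenously (IV) or inhaled, respectively, with a range of 18 to 33 hours". Protocol 4.1 cites a single-dose study of dronabinol, with a mean half-life "of 5.5 hours. This data supports the twice daily dosing of Cannabidiol Oral Solution", and does not mention the cannabidiol figure.

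**The concern.** After a dose change, the plasma level takes several half-lives to reach its new plateau. A sample drawn before then reflects partly the old dose. If it is filed under the new dose, it reads too high after a reduction and too low after an increase. Dividing by the new dose leaves the relative error unchanged.

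Two outputs are exposed. The by-dose summaries mix settled and unsettled samples. RCtrough is more sensitive, because Visit 5 is the denominator of every later ratio: one unsettled Visit 5 sample shifts all of that subject's ratios, and the shift looks like accumulation or its opposite. Monitoring changes in plasma levels during long-term treatment is a stated objective (protocol 2.1), and RCtrough is the PK SAP's measure of accumulation.

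**Working it through.** The documents state no time to steady state, so there is no figure of the plan's own to reproduce.

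**Inputs from the documents**
- Cannabidiol half-life h: 18 to 33 hours (protocol 1.1.4.1).
- Dronabinol half-life: 5.5 hours (protocol 4.1), for comparison only.
- Visit windows: Week 2 ±3 days; Weeks 4 and 8 ±7 days (protocol Table 1).

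**Assumptions**
- Linear, one-compartment, first-order kinetics.
- A halving or doubling of the dose; the documents give no step sizes.
- The 18 to 33 hour range applies to this product and population.

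**Plausibility of the half-life.** Protocol 1.1.4.1 also says: "Cannabidiol is cleared from plasma at rates between 960 and 1560 mL/min and the distribution volume is estimated to be approximately 30 L/kg". With h = ln 2 × V / CL and an assumed 70 kg adult, V = 30 × 70 = 2,100 L. CL is 960 mL/min = 57.6 L/h, or 1,560 mL/min = 93.6 L/h. So h = 0.693 × 2,100 / 57.6 = 25.3 h, or 0.693 × 2,100 / 93.6 = 15.6 h. This overlaps 18 to 33 hours and is far from 5.5.

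**Time to steady state.** Five half-lives complete 1 − 2^(−5) = 96.9% of a change.
- 18 h: 90 h = 3.75 days
- 33 h: 165 h = 6.9 days
- 5.5 h: 27.5 h = 1.15 days

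**Error in the dose-normalised trough.** The part of the change still outstanding after time t is r = 2^(−t/h). Relative to its true steady-state value, the trough reads 1 + r after a halving and 1 − r/2 after a doubling.

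| Days since change | Halving, 18 h | Halving, 33 h | Doubling, 18 h | Doubling, 33 h |
|---|---|---|---|---|
| 1 | +40% | +60% | −20% | −30% |
| 2 | +16% | +36% | −8% | −18% |
| 3 | +6% | +22% | −3% | −11% |
| 4 | +2% | +13% | −1% | −7% |
| 7 | +0.2% | +3% | −0.1% | −1.5% |

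At 5.5 hours the one-day errors would be +5% and −2%.

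**Effect on RCtrough.** If Visit 5 falls one day after a halving, every later ratio is multiplied by 1/1.397 = 0.72 (18 h) to 1/1.604 = 0.62 (33 h). One day after a doubling, the factor is 1/0.802 = 1.25 to 1/0.698 = 1.43.

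**Which samples are exposed.** For changes made at scheduled visits, the shortest gap from Visit 4 to Visit 5 is (28 − 7) − (14 + 3) = 4 days. From Visit 5 to Visit 6 it is (56 − 7) − (28 + 7) = 14 days, when r at 33 h is 2^(−336/33) = 0.0009. Otherwise only changes between visits matter. If these were spread evenly (an assumption), 7/28 = 25% of those in a 4-week interval and 7/84 = 8% of those in a 12-week interval would fall within 7 days of the next sample. The mean error after a halving is about (h/ln 2) / interval. With h/ln 2 = 0.75/0.693 = 1.08 days (18 h) and 1.375/0.693 = 1.98 days (33 h), that is 3.9 to 7.1% over 28 days and 1.3 to 2.4% over 84 days. After a doubling it is half as large, with the opposite sign. These are averages over samples preceded by a change in that interval, not over all samples.

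**The case against.** **The half-life is not for this product.** The 18 to 33 hours come from IV and inhaled use. Protocol 1.0 says that its overviews describe other, primarily plant-based formulations, and protocol 1.1.4.2 says: "Cannabidiol PK has not previously been studied in a pediatric population". This stands. The magnitudes are conditional, and the 7-day limit is a stated assumption. It does not remove the gap, because some settling time applies on any half-life and the PK SAP sets none.

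**The average effect is small.** This stands too. The large errors belong to the first days after a change, the study is descriptive, and no hypothesis is tested. Individual plots are to show the dose at each sample where possible, listings carry dose and time post dose where available, and a population PK model may use the data later. None of these protects the by-dose summaries or RCtrough, and the listings carry no time since the last change.

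**Stronger readings that a reader might infer**
- That the 5.5-hour figure undermines twice-daily dosing. A longer half-life does not contradict that interval, and the protocol uses 5.5 hours for nothing else. No passage ties it to the sampling times or to the missing rule.
- That the tables would present unsettled values as steady-state results. The steady-state label is the protocol's; the PK SAP calls the samples pre-dose troughs. The fault lies in combining that endpoint with assignment to the current dose and no stability rule.
- That many samples are affected. The documents give no frequency or timing of dose changes, so no count can be derived.

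**Conclusion.** The point holds as a gap in the PK SAP. Followed as written, it produces biased entries in the by-dose summaries and RCtrough for any sample taken within about 4 to 7 days of a dose change. The one-day error is +40 to +60% after a halving and −20 to −30% after a doubling, falling to at most about 3% at 7 days. An affected Visit 5 sample carries its error into all of that subject's later ratios.

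This rests on linear one-compartment kinetics, on changes by a factor of two, and on an 18 to 33 hour half-life not established for this oral solution in children. The documents give no half-life for the 7-OH metabolite, so the figures are for the parent drug only. The number of affected samples is unknown and probably small. Adverse events, the primary outcome, are unaffected.

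The difference between protocol 4.1 and 1.1.4.1 is a separate, minor matter of wording.

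**What to change.** In the PK SAP:

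1. Derive the time since the last dose change for each sample. SAP Section 14 already needs dated dose records to report the total duration of each dose, so no new data collection should be needed.
2. Flag samples with less than 7 days on the current dose (5 × 33 h = 6.9 days), and state the half-life as an assumption.
3. Leave flagged samples out of the steady-state by-dose summaries and RCtrough. Keep them in the listings, and add a sensitivity table using all samples.

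The cost is one derived variable, one rule and one extra table. A few samples leave the main tables, and a subject whose Visit 5 sample is flagged has no RCtrough there; the sensitivity table still shows it.

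In the protocol, reconcile Sections 4.1 and 1.1.4.1 so that the text explains how the dronabinol and cannabidiol half-lives relate. This is a wording change; no dose or dosing interval is proposed.

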4.1.1 Dose Adjustments

IP dose may be adjusted at the investigators discretion. Dose may be adjusted up or down based on efficacy, safety or tolerability. All dose changes must be clearly documented in the eCRF. Maximum dose must never exceed 40mg/kg/day.

4.1.2 Dose Tapering

If the subject is not going to continue to receive IP offered under the Investigator IND Expanded Access Program, the subject may be tapered off Cannabidiol Oral Solution based on the investigator's preference and subject's tolerability. The investigator should ensure that the taper is planned well in advance to allow sufficient time to complete the taper prior to the Visit 10 at 48 weeks (± 10 days). The date of entering the Expanded Access Program will be documented in the EDC.

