6.1.6 Safety-related Endpoints

The safety-related endpoints are:

- Incidence, type, and severity of AEs and SAEs associated with Cannabidiol Oral Solution as an adjunctive treatment for seizures
- Changes from baseline in the previous study in vital signs
- Changes from baseline in the previous study in ECG findings
- Changes from baseline in the previous study laboratory values (hematology, chemistry, and urinalysis).

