Subjects will receive twice daily oral doses of Cannabidiol Oral Solution for approximately 48 weeks or until the IP is successfully approved for marketing in the US (whichever occurs earlier), inclusive of their treatment on the previous study. For subjects that completed INS011-14-029, 48 weeks of treatment would be completed under this protocol. For subjects that participated in INS011-15-054, duration of treatment in INS011-14-030 will be based on the length of time they were enrolled in INS011-15-054 such that total duration of treatment in both studies combined will not exceed approximately 48 weeks. Subjects visit entry into INS011-14-030 will be determined at the discretion of the sponsor and the investigator. All subjects will complete the Final Visit/Discontinuation Visit regardless of when they stop treatment/complete the study. A Follow-up Visit will occur 2 weeks after the Final Visit/Discontinuation Visit.

If the subject is not going to continue to receive IP offered under the Investigator IND Expanded Access Program, the subject may be tapered off Cannabidiol Oral Solution based on the investigator's preference and subject's tolerability. The investigator should ensure that the taper is planned well in advance to allow sufficient time to complete the taper prior to the Visit 10 at 48 weeks (± 10 days). The date of entering the Expanded Access Program will be documented in the electronic case report form (eCRF).

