3.3. CHANGES TO ANALYSIS FROM PROTOCOL

Given that an Investigator may choose to down-titrate or up-titrate subjects to any dose, results will not be analyzed and presented "by dose and overall" as currently stated in the protocol. It has been agreed with Insy (13Oct2016) that summaries will only be presented by age category and overall as described in this SAP ([Sections 9 to 17](#)).

Document: C:\Users\q832483\Documents\Insy CSR\Pending\Ready for QC\New folder\Statistical Analysis Plan.docx
Author: [REDACTED] Version Number: V1.0 Final
Version Date: 04APR2017

Template No: CS_TP_BS016 – Revision 3
Effective Date: 01May2012

Reference: CS_WI_BS005

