6.3. RETESTS, UNSCHEDULED VISITS AND EARLY TERMINATION DATA

For by-visit summaries, data recorded at the nominal visit will be presented. Unscheduled measurements will not be included in by-visit summaries, but will contribute to the best/ worst case value where required (e.g. shift table).

In the case of a retest (same visit number assigned), the earliest available measurement for that visit will be used for by-visit summaries.

If the retest measurement occurs prior to the dosing of the first study medication, the retest measurement will be used in the summary statistics if it is the last measurement taken prior to the dose. The retest measurements will not be used in summary statistics for post dose measurements.

Early termination data will be mapped to the next available visit number for by-visit summaries.

Listings will include scheduled, unscheduled, retest and early discontinuation data.

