17.4. ECG EVALUATIONS

Results from the central electrocardiogram (ECG) review will be included in the reporting of this study. If the first ECG is abnormal, up to an additional 2 repetitions of a specific assessment may be performed. ECG will be evaluated at Screening (for subjects who did not meet the rollover timing criteria, see [Section 6.2](#)), Day 1 and at Final Visit/Discontinuation Visit.

The following ECG parameters will be reported for this study:

- HR (Ventricular rate) (bpm)
- PR Interval (msec)
- QRS Interval (msec)
- QT Interval (msec)
- QTcF Interval (msec) [QT interval corrected by Fridericia]
- RR Interval (msec)
- Rhythm
 - Sinus rhythm
 - Atrial fibrillation
 - Other
- Overall assessment of ECG (Investigator's judgment):
 - Normal
 - Abnormal, Not Clinically Significant (ANCS)
 - Abnormal, Clinically Significant (ACS)

Handling of retests values is described [Section 6.3](#).

Document: C:\Users\q832483\Documents\Insy CSR\Pending\Ready for QC\New folder\Statistical Analysis Plan.docx
Author: [REDACTED] Version Number: V1.0 Final
Version Date: 04APR2017

Template No: CS_TP_BS016 – Revision 3
Effective Date: 01May2012

Reference: CS_WI_BS005

The following summaries will be provided for ECG data:

- Frequency counts and shift from baseline by age category (for qualitative measurements) in separate tables
- Summary of absolute results and change from baseline by age category (for quantitative measurements) in separate tables
- Absolute value and change from baseline according to markedly abnormal criteria and age category as described in [Section 17.4.1](#)
- Listing of all data with flag for subjects meeting markedly abnormal criteria for absolute values and for change from baseline

Each ECG result will be compared to the both baselines as defined [Section 6.2](#).

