17.4.1. ECG MARKEDLY ABNORMAL CRITERIA

Markedly abnormal quantitative ECG measurements will be identified in accordance with the following predefined markedly abnormal criteria and summarized by time point and age category for QT interval and QTcF parameters.

- Absolute values for QT interval and QTcF will be classified as:
 - > 450 msec
 - > 480 msec
 - > 500 msec
- Change from Baseline for QT interval and QTcF will be classified as:
 - >30 msec increase from baseline
 - >60 msec increase from baseline

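### Visit 10 ECG and VABS results of subjects tapered off before that visit are pooled with those of still-dosed subjects, with no planned split by dosing status

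*Protocol*

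**What the plan says.** Protocol 4.1.2 (Dose Tapering) applies to subjects who will not go on receiving the product under Expanded Access. The taper is optional: "the subject may be tapered off Cannabidiol Oral Solution based on the investigator's preference and subject's tolerability". Where it is used, the investigator is asked to ensure that "the taper is planned well in advance to allow sufficient time to complete the taper prior to the Visit 10 at 48 weeks". SAP 3.1 repeats this, asking for "sufficient time to complete the taper prior to the Visit 10 at 48 weeks". Visit 10 can therefore contain tapered subjects alongside subjects still on drug.

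SAP 3.3 withdraws the protocol's by-dose presentation: "summaries will only be presented by age category and overall as described in this SAP". SAP 6.3 adds: "For by-visit summaries, data recorded at the nominal visit will be presented".

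After any Screening assessment, SAP 17.4 places the ECG at "Day 1 and at Final Visit/Discontinuation Visit". SAP 17.4.1 has markedly abnormal values "summarized by time point and age category for QT interval and QTcF parameters". Protocol 6.1.6 lists among the safety endpoints "Changes from baseline in the previous study in ECG findings". Footnote p to Protocol Table 1 limits VABS to Visits 2 and 10.

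SAP 7.4 defines a CBD status, continuing or stopping after the Final visit. It is applied to the follow-up period and the Follow-up visit, not to Visit 10.

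**The concern.** The final visit of a long-term safety study will normally be read as the state of subjects after about 48 weeks on drug. For a subject whose taper was completed as planned, it is a reduced-dose or off-drug observation. If the pooled table shows no shift in QTcF, the reader cannot tell how much of that comes from subjects still exposed. If it shows a shift, the reader cannot tell whether it belongs to exposure or to withdrawal.

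ECG and VABS stand out because each has a single scheduled value after Day 1. No earlier on-treatment visit in this study can stand in for it.

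**Working it through.** The plan states no figure to reproduce, and SAP 6.5 rules out inference. The check compares the schedule with the planned tables.

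**Step 1. Scheduled assessments after Day 1, up to and including Visit 10** (Protocol Table 1, Protocol 5.2.3, SAP 16.2.1):

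| Assessment | Visits | Visit 10 share |
|---|---|---|
| ECG | 10 | 1 of 1 |
| VABS | 10 | 1 of 1 |
| Seizure diary week | 8, 9, 10 | 1 of 3 |
| CGI and IPES | 5, 6, 7, 8, 9, 10 | 1 of 6 |
| Hematology and chemistry, Table 1 | 8, 9, 10 | 1 of 3 |
| Hematology and chemistry, adding Protocol 5.2.3 | 5, 6, 8, 9, 10 | 1 of 5 |

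Table 1 and Protocol 5.2.3 disagree on the Visit 5 and 6 blood draws, so both counts are shown.

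**Step 2. Is there a split by dosing status at Visit 10?**

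- ECG (SAP 17.4, 17.4.1): by age category; no CBD-status table.
- VABS (SAP 17.7.3): by age category, with CBD status at the Follow-up visit. Table 1 and Protocol 5.4 schedule no VABS there, so that split would be empty for VABS.
- CGI, IPES and laboratory (SAP 16.2.2.3, 17.3): CBD status at the Follow-up visit only.
- Seizures (SAP 16.2.1.3): by time point and age category. One figure also uses modal dose, a whole-study label and not status at the visit.
- Plasma levels (PK SAP): Expanded Access subjects are flagged at Visits 10 and 11 and summarised in secondary tables, and concentrations are tabulated by the dose at sampling. The main SAP has no counterpart.

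**Step 3. What the ECG change measures.** SAP 6.2 defines two baselines. Baseline 1 comes from the previous study. Baseline 2 is the last value before the first dose in this study, which may be Day 11 of INS011-14-029. Protocol 3.1 intends rollover without interruption of drug, so for a direct rollover Baseline 2 may be an on-drug value. For a tapered completer, change from Baseline 2 may then run from on drug to off drug.

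**Step 4. Ceilings** (Protocol 3.4). ECG: 60 + 20 = 80 subjects. VABS: 80 − 20 = 60, because subjects from INS011-15-054 are excluded from it.

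**Step 5. Illustration on assumed shares.** The tapered share f is not in the documents. Suppose all 80 subjects have a Visit 10 ECG and none shows a given QTcF abnormality. The one-sided 95% upper bound is 1 − 0.05^(1/n), with n = 80 × (1 − f) still dosed:

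| Assumed f | n still dosed | Upper bound |
|---|---|---|
| 0% | 80 | 3.7% |
| 10% | 72 | 4.1% |
| 25% | 60 | 4.9% |
| 50% | 40 | 7.2% |

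The pooled table would be read at the first line whatever f is. This shows only how the reading depends on f; it does not estimate f.

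**The case against.** The strongest reply is that the number affected may be small or nil. The taper is optional, concerns only subjects not entering Expanded Access, and came with Amendment 5 (06 March 2017), so Visit 10s held before then are outside the point. A taper ending just before Visit 10 may leave drug on board. This stands, and it is why no size or direction is claimed.

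A second reply is that the data are recoverable. SAP 14 lists first and last dose dates, assessment listings carry study day, and ECG data are listed with flags. That is true, but listings do not correct the summary tables.

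A reader might also infer more than the documents support:

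- *That tapered subjects have no on-drug ECG.* A direct rollover's Day 1 ECG may be on drug and can be compared with Baseline 1. The possible loss is the late ECG.
- *That all Visit 10 results are pooled.* The PK SAP separates plasma levels.
- *That the modal-dose figure fails because of tapering.* The mismatch arises with any dose change, which Protocol 4.1.1 allows throughout.
- *That CBD status leaves tapered subjects unclassified.* Read literally it has no place for someone who stopped before the Final visit, but the natural reading puts them with those not receiving drug. The gap is mostly wording.
- *That no table separates adverse events arising after the last dose but before Visit 10.* The text describes none; table content also depends on templates not available here.

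**Conclusion.** The point holds, most clearly for ECG and VABS. Followed as written, the plan pools a tapered completer's only scheduled post-Day 1 ECG and only post-baseline VABS with those of still-dosed subjects, and the QT/QTcF categories inherit the mixture. This assumes that at least one subject is tapered as Protocol 4.1.2 describes and attends Visit 10.

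For the final diary week, CGI, IPES and laboratory values the same mixing occurs but matters less. Earlier on-treatment visits remain, and the efficacy data are descriptive and not endpoints.

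It would be tempting to conclude that the Visit 10 ECG tables understate a drug effect by a calculable amount. The documents do not support that: they give neither the tapered share nor the interval from last dose to Visit 10. The half-lives in Protocol 1.1.4.1 are for intravenous or inhaled cannabidiol and come from other formulations. No test or error rate is affected. This is a cheap improvement to the reporting of a declared safety endpoint, not evidence that the study's safety conclusion is wrong.

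**What to change.** Leave the taper as it is and change the analysis only.

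1. From the last-dose date (SAP 14) and the recorded dose changes (Protocol 4.1.1), derive dosing status at Visit 10: still dosed and not in the end-of-study taper, versus tapering or off drug. Record days since last dose.
2. Show Visit 10 ECG, including the SAP 17.4.1 QT/QTcF categories, and VABS by that status beside the planned overall tables, using observed values.
3. Flag the same status for Visit 10 seizure, CGI, IPES and laboratory results, without a full set of extra tables.
4. Reword CBD status in SAP 7.4 so that subjects who stopped at or before the Final visit are explicitly classified.
5. Identify treatment-emergent events with onset after the last dose but before Visit 10.

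The cost is SAP wording, one derived variable with its day count, and a few added displays from data already collected. There are three downsides. Cells will be small, from at most 80 subjects for ECG and 60 for VABS. Status is chosen after baseline, so the split is descriptive and cannot by itself separate a withdrawal effect from other differences between the groups. SAP 14 has no reason code for a taper, so its start may have to be inferred and could be confused with a dose reduction for another reason.
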